Trajectory of Recovery in the Elderly (TORIE)

PI: [name]

NCT02275026

Document Date: 10-31-2013

protocols and forms will be compiled into an operations manual that will be revised as necessary. The manual will include a question-by-question written script for interviewing purposes. Neuropsychological assessment will be conducted by specially trained personnel with experience in psychological assessment. Training will be conducted, as part of the overall investigators' training meeting, by Drs. [name]. Training seminars will be repeated every six months and as needed, to ensure standardization of procedures.

Data Reliability: Diagnostic, case ascertainment and methodologic consistency will be assured by implementing at least every six month training sessions for all the staff. An initial training meeting before study enrollment, and monthly conferences thereafter will ensure reliability and consistency in the use of diagnostic criteria and written standard operating procedures. All data will be independently audited to confirm consistency among participant records, study data sheets, and the main database. Additionally, we will use standard statistical and graphical methods to identify outlying data and confirm their validity

Data will be maintained in a custom-designed relational database (Research Electronic Data Capture REDCap). The REDCap Consortium is composed of 549 active institutional partners from CTSA, GCRC, RCMI and other institutions in 50 countries. The consortium supports a secure web application (REDCap) designed exclusively to support data capture for research studies.

Although the current proposal is not a clinical trial, we will incorporate a **Data and Safety Monitoring Plan** with a **Data and Safety Monitoring Board** (DSMB) as described in the section E.

10. Data Analysis

All analyses will use a type I error of 5% (two-sided) to test for statistical significance, and will be performed using SAS v9.3 (SAS Institute Inc., Cary, NC). The fit of all models to the data will be examined using standard approaches, such as examination of residuals and the proportional hazards assumption for Cox regression. All baseline and outcome data on participants enrolled in this study will be summarized. Categorical variables will be described in terms of counts and percentages, and quantitative variables in terms of medians and ranges or means and standard deviations, as appropriate.

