10.1 Specific Aim I: *The primary goal is to test whether age is associated with the time of return to baseline cognitive function, assessed by PQRS (primary) and NIH toolbox (secondary), following general anesthesia.*

Scales of the PQRS are performed prior to anesthesia, and then following anesthesia at defined time intervals (see Section 4). We will focus on the recovery of cognitive function (the primary endpoints as described in 5.0) as related to age and controlling for other participant characteristics using Cox discrete time regression.⁷⁴ We expect that everyone will return to baseline cognitive function by 30 days, most early in the course of testing. Thus, if later time points are missing most will have been observed before loss to follow-up. For intermittent missingness before returning to baseline, we will truncate the observations at the time of missing observations. In a subsequent sensitivity analysis, we will assume that they are missing at random and use last value carried forward (worse-case scenario). We will also explore multiple imputation if >5% of the outcome data are missing prior to returning to baseline function.

For the secondary NIH Toolbox outcomes, we will calculate six primary standard Adjusted Scale Scores, as described in the Scoring Manual for Toolbox measures described in 5.1. We will again use discrete time Cox regression with covariate adjustment; however, the granularity of the timing of measurements is less than the primary outcome of PQRS. For both the primary and secondary outcomes, we will use the Hochberg test to adjust for multiple comparisons.⁷⁵

To study the time course of the PQRS and Toolbox measures, we will use generalized linear mixed models (GLMMs),⁷⁶ which account for the covariance structure of repeated observations within participant, and we will test whether a random intercepts and slopes for participants best fit the data. GLMMs are statistical models for data with correlations or non-constant variability and where the response is not necessarily normally distributed. GLMMs assume that missing data are missing at random; thus, participants with partial data contribute to the model estimation. We will fit the appropriate distribution (e.g. dichotomous, count, ordinal, normal) for each outcome using Proc GLIMMIX in SAS v9.3.

10.2 Specific Aim II: *The measures for fMRI analyses generally fall into three groups: resting, task-driven, and rCBF.*

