Change scores will be calculated for each of 20-25 components (characterizing resting state and activity driven brain networks) related to fMRI imaging at each time point (Section 4). These changes (expressed in standardized units) associated with age will be analyzed using GLMMS adjusted for participant characteristics as described for Aim 1. We will use the False Discovery Rate test to adjust for multiple comparisons.⁷⁷

For the ASL analysis, an additional 5 measures for rCBF (global and right/left frontal and temporal) will be generated for each of three time points and analyzed with GLMMS corrected for multiple comparisons as described above.

fMRI components will be entered as covariates in the above-mentioned Cox discrete-time models for the primary outcomes (PQRS and NIH Toolbox scales) to assess their association with the primary outcomes and with age. Similarly, the fMRI components will be entered into the GLMMS described in 10.1 to estimate their adjusted associations. We will use the False Discovery Rate test to adjust for multiple comparisons.⁷⁷

10.3 Sample Size, Power, and Effect Size Estimation:

Sample and power for secondary outcomes were calculated with PASS12 (PASS12, Kayville, Utah, USA). **SA1:** A Cox regression⁷⁸ on the time to return to baseline cognitive performance requires 72 participants to detect a HR of 1.03 per year or age ($\beta=0.033$), assuming a standard deviation for age of 11.25 years, 80% power, a Type I error of 0.05, and adjusting for other characteristics expected to have a generalized R^2 of 0.2.⁷⁹⁸⁰

The NIH toolbox yields six primary standardized scaled scores (mean=100, SD=15). Although there will be fewer discrete time measurements for Cox regression, the effect-size calculation is similar. Assuming 72 participants with a standard deviation for age of 11.25 years, an adjusted Type 1 error rate of $0.05/6=0.0083$, and other covariates having a generalized R^2 of 0.2 with age, a HR of 1.04 ($\beta=0.041$) can be detected with 80% power.⁸⁰

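### The SAP scores the NIH Toolbox outcomes as Adjusted Scale Scores without saying what they are adjusted for; if for age, the Toolbox mixed models lose the age effect on score level and may distort the age-by-time effect.

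*SAP*

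**What the plan says.** SAP 10.1 states the aim: "The primary goal is to test whether age is associated with the time of return to baseline cognitive function". PQRS is primary and the NIH Toolbox secondary. On Toolbox scoring it says: "For the secondary NIH Toolbox outcomes, we will calculate six primary standard Adjusted Scale Scores, as described in the Scoring Manual". SAP 10.3 gives the metric as mean 100 and SD 15.

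The Toolbox scores enter two kinds of analysis in 10.1:

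- Time to return to baseline: "We will again use discrete time Cox regression with covariate adjustment".
- Time course: generalized linear mixed models (GLMMs) on the repeated scores. The Protocol's data collection table places these before the procedure and at 1, 7 and 30 days.

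SAP 10.2 then enters the fMRI components into both kinds of model.

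The supplied text does not say what the scores are adjusted for, whether the norms are age-specific, or whether unadjusted scores will also be analysed. It gives no numerical rule for return to baseline on the Toolbox. SAP 5.0 and 5.1 and the Scoring Manual are cited but are not in the supplied text.

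**The concern.** When age is the predictor, the reader needs to know whether age has already been taken out of the outcome. A normed scale leaves this open: mean 100 and SD 15 could refer to the whole population or to people of the participant's own age. The Protocol (Study Timelines) says the instrument covers ages 3 to 85 and values it for studying function across the lifespan. Scoring within age would work against that use.

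If the norms are age-specific, a Toolbox analysis showing no age trend could reflect the scoring and still be read as evidence that older volunteers perform or recover like younger ones. If the adjustment also covers other demographics, adding those characteristics as covariates accounts for them a second time.

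**Working it through.** **1. The plan's own figure.** Inputs from SAP 10.3 are β = 0.041 per year of age, age SD 11.25, R² = 0.2, two-sided alpha 0.05/6 and power 80%. All participants are expected to return by 30 days, so the event proportion is 1.

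N = (z for alpha/2 + z for power)² / [SD² × β² × (1 − R²)] = (2.638 + 0.842)² / (126.56 × 0.001681 × 0.8) = 12.11 / 0.1702 = 71.1, rounded up to 72.

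This reproduces the SAP. The formula contains no term for the score scale, so the sample size does not depend on how the Toolbox is scored.

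**2. What age norming does.** Assume the adjusted score is 100 + 15 × (raw − μ(age)) / SD(age), where μ and SD are the norm mean and SD at that age.

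- Level: if the sample follows the norm curve, the expected score is 100 at every age and the age slope is zero.
- Change, with the participant on one norm throughout: μ cancels and adjusted change = raw change × 15 / SD(age).

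**3. Level, simulated.** Ages were uniform over 40.5 to 79.5 (SD 11.25). Assumed raw slopes of 0, −0.3, −0.6 and −0.9 points per year gave adjusted slopes of about 0.00 in every case. Over the 40 years from 40 to 80, a raw slope of −0.6 is a 24-point difference (40 × 0.6) that the adjusted score does not show.

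**4. Change.** None of these inputs is in the documents. Assume raw day-1 change = −3 − 0.10 × (age − 60), which is −1 at age 40 and −5 at age 80. Let the norm SD run linearly from 15 at age 40 to 15 × ratio at age 80. Adjusted change is then −1 at age 40 and −5 / ratio at age 80.

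| SD at 80 ÷ SD at 40 | Adjusted change at 80 | Age slope = (change at 80 + 1) / 40 |
|---|---|---|
| 0.8 | −6.25 | −0.13 |
| 1.0 | −5.00 | −0.10 (same as raw) |
| 1.25 | −4.00 | −0.075 |
| 1.5 | −3.33 | −0.06 |

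Simulation gave −0.13, −0.10, −0.07 to −0.08, and −0.06. With a constant norm SD, change is only multiplied by a constant and its test is unaffected.

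**5. Return to baseline.** At a fixed age, norming preserves order. A score at or above the participant's own baseline on the raw scale is so on the adjusted scale too; simulated agreement was 100%.

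With an assumed margin of 7.5 scaled points, the raw margin is 7.5 × SD(age) / 15. At age 80 that is 6.0, 7.5, 9.4 and 11.25 raw points for the four ratios. Agreement between raw and adjusted events was about 96%, 100%, 95% and 91%. Among simulated participants over 70, about 69% counted as returned on the raw scale, against about 61%, 69%, 78% and 85% on the adjusted scale.

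**The case against.** The strongest objection is that the premise is not in the documents. Nothing supplied says the adjustment includes age, and a mean of 100 with SD 15 fits whole-population norming equally well. SAP 5.1 or the manual may settle it. This stands: a reader might infer that the SAP has regressed age on an age-free score, but the text shows only an unstated definition.

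Second, Aim I is about time to return, and a strict within-person rule is immune to norming. This also stands. A reader might infer that the trial's main age contrast is biased. It is not: PQRS is primary and is not a Toolbox score, and the Toolbox Cox analysis is at risk only under a points-based margin, which the supplied text does not state.

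Third, the GLMM paragraph in 10.1 speaks of time course and does not spell out a test of age on level. That is fair, but age is the stated exposure of the aim, and a time-course model with age in it will yield an age coefficient that someone will read. For the same reason, expressing the problem as lost power for a cross-sectional age slope would go too far: the SAP neither specifies nor powers that test.

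Fourth, if age is in the model and the norming is linear in age with constant SD, the age-adjusted fMRI coefficients in 10.2 do not change. Correct. There the exposure is in the age coefficient, in models without age, and where norm SD varies with age.

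Finally, the direction of any distortion in change is unknown. The table shows it can go either way, and the documents support neither direction.

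**Conclusion.** The concern holds as a conditional point about a secondary outcome. The SAP leaves the adjustment undefined. If it includes age, the Toolbox GLMMs cannot show an age effect on score level except where this sample departs from the norm's age curve. The age-by-time slope is distorted if the norm SD varies with age: by about 30% upwards to 40% downwards in the assumed cases (−0.13 and −0.06 against −0.10). A points-based return margin would then mean different raw losses at different ages.

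The size rests on assumed declines and SD ratios; the mechanism follows from the scoring formula. If the adjustment excludes age, this problem disappears. Nothing here touches the PQRS analysis, the sample of 72 inflated to 76, or a Toolbox return rule of at or above own baseline.

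**What to change.** In SAP 10.1:

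- State what the Adjusted Scale Scores are adjusted for.
- Fit the Toolbox GLMMs, including the 10.2 versions with fMRI components, to scores not normed for age or demographics. These can be raw scores or scores standardized once to the whole sample. Age and the other characteristics enter as model covariates.
- Keep the Adjusted Scale Scores for describing the sample at baseline, or as a sensitivity analysis.
- State the Toolbox return-to-baseline rule, and apply any margin in points on the unadjusted scale.

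The cost is a few sentences in the SAP and a different score derived from the same test data. Unadjusted scores will show somewhat more between-person spread, which age as a covariate and the participant random effects should largely absorb. If the adjustment turns out to exclude age, the change does no harm.

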### e) Study Endpoints

The primary endpoint is return to baseline cognitive function.

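### Does the Hochberg sentence in SAP 10.1 undermine the 80% power that SAP 10.3 states for PQRS?

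*SAP*

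**What the plan says.** SAP 10 opens with a general rule: "All analyses will use a type I error of 5% (two-sided) to test for statistical significance". SAP 10.1 ranks the Aim 1 outcomes, "assessed by PQRS (primary) and NIH toolbox (secondary", and later remarks that for the Toolbox "the granularity of the timing of measurements is less than the primary outcome of PQRS". It then states the multiplicity rule: "For both the primary and secondary outcomes, we will use the Hochberg test to adjust for multiple comparisons". It names no family and gives no testing order. Earlier in 10.1 the PQRS analysis refers to "the primary endpoints as described in 5.0", in the plural; Section 5.0 is not in the extract.

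SAP 10.2, introducing the imaging covariates, loosely groups PQRS and the Toolbox scales together as primary outcomes.

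SAP 10.3 sizes PQRS with "80% power, a Type I error of 0.05, and adjusting for other characteristics", giving 72 participants. For the six Toolbox scores it uses "an adjusted Type 1 error rate of" 0.05/6 = 0.0083 with the same 72. Enrolment is then raised to 76 to allow for missing data.

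Protocol 5(e) uses the singular: "The primary endpoint is return to baseline cognitive function".

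**The concern.** Read literally, the Hochberg sentence covers primary and secondary outcomes in one breath, and the loose label in 10.2 lends some support to pooling them. Hochberg compares the largest p-value with 0.05, the next with 0.025, and so on down to 0.05 divided by the number of tests. In a pooled family of seven, a single Toolbox score with p above 0.05 means PQRS must reach at most 0.025. A secondary result would then raise the bar for the primary test. SAP 10.3 makes no allowance for that, so its 80% would be overstated. A PQRS p-value of 0.03 could count as significant or not depending on which reading the analyst took. The plural in 10.1 raises a second possibility, that there are several PQRS tests, in which case an unadjusted 0.05 would also be too generous.

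**Working it through.** **Inputs (SAP 10.3).** SD of age 11.25 years; generalized R² 0.2; 80% power; PQRS β = 0.033 at α = 0.05; Toolbox β = 0.041 at α = 0.05/6; n = 72. Every participant is taken to have the event, since the SAP expects all to be back at baseline by 30 days.

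**Formula.** n = (z₁₋α/₂ + z₀.₈)² / (SD² × β² × (1 − R²)).

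**Reproducing the plan.**
- PQRS: (1.960 + 0.842)² / (126.56 × 0.001089 × 0.8) = 7.849 / 0.1103 = 71.2, so 72. Power at 72 is 80.4%.
- Toolbox: (2.638 + 0.842)² / (126.56 × 0.001681 × 0.8) = 12.11 / 0.1702 = 71.1, so 72. Power at 72 is 80.6%.

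**Which layout do these figures fit?** The smallest PQRS β detectable with 80% power at n = 72 is:

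| Lowest Hochberg threshold | Layout | Detectable β |
|---|---|---|
| 0.05 | one PQRS test, own family | 0.0328 |
| 0.025 | two PQRS tests | 0.0361 |
| 0.05/7 | PQRS pooled with six Toolbox scores | 0.0414 |

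The SAP states 0.033, which matches only the first row. The Toolbox β does not discriminate, because 0.05/6 gives 0.0408 and 0.05/7 gives 0.0414, and both round to 0.041. The stated divisor does: it is 6, not 7.

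**Under two families.** Hochberg on a single test is that test at 0.05, so PQRS keeps 80.4%. For the Toolbox, 0.05/6 is the lowest threshold Hochberg can impose, so 80.6% per score is a floor.

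**Under one pooled family of seven.** These are simulations with 400,000 runs, PQRS β = 0.033 and equally correlated normal statistics. The correlation is an assumption.

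| Toolbox effects | PQRS power, n = 72 |
|---|---|
| all six β = 0.041 (the SAP's value) | 76-77% at correlation 0 to 0.7; 79-80% at 0.9 |
| five at 0.041, one null | 69-71% |
| all six β = 0.033 | 68-70% |
| all six null | 55% |

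With all 76 enrolled participants evaluable, the first row becomes 79-80% at correlation 0 to 0.5 and the last 58%. At the lowest threshold, 0.05/7, 80% power for PQRS would need 12.47 / 0.1103 = 113.1, so 114 participants. Toolbox power hardly moves: 79.1% at 0.05/7.

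**Error across both families.** With two separate families and no gate, the chance of any false positive is at most 1 − 0.95² = 9.75% if the two families are independent; simulation gives 8-10% at correlation 0.5 to 0. One pooled family gives 4-5% over the same range. Gating the Toolbox on PQRS would hold it at 5%, but average Toolbox power at β = 0.041 would drop from 92% to 74% at correlation 0, and from 90% to 76% at 0.5.

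**The case for a change.** The best case for a change is that the sentence as written is either empty or wrong for the primary outcome. With one PQRS test alone in its family, Hochberg has nothing to adjust. With several PQRS tests, or with pooling, the unadjusted 0.05 in 10.3 does not fit. An analyst could defend pooling from the wording of 10.1 and the label in 10.2, and could in principle choose after seeing p-values. A clarifying sentence would cost nothing.

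Part of this stands: 10.1 does not name the families, and 10.2 uses the word primary loosely. The rest is weaker. The sentence still does real work for the six Toolbox scores. The primary and secondary labels, the singular wording for PQRS in 10.1 and in Protocol 5(e), the unadjusted 0.05 and the divisor of 6 all agree with one another. Against them stand one plural and one loose label. The several-tests possibility cannot be judged here, because Section 5.0, to which 10.1 refers for the primary endpoints, is not in the extract; any number of PQRS tests would be a guess. Finally, an explicit statement that the Toolbox is tested whatever the PQRS result would go beyond clarification. Gating trades overall error against Toolbox power, and statisticians reasonably differ on it for secondary outcomes.

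**Conclusion.** No change is called for. The plan leaves the Hochberg families unnamed, but its own significance levels identify them: PQRS as one test at two-sided 0.05, and Hochberg within the six Toolbox scores. An analyst following 10.3 would fill the gap that way, and the stated 72 and 80% then hold by the SAP's own formula.

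The pooled reading would cost PQRS 3 to 4 percentage points at the SAP's effect sizes (n = 72, correlation 0 to 0.7), and about 10 if one Toolbox score is null. That loss arises only on the reading the documents support least.

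Two assumptions carry the conclusion: that Section 5.0 defines a single PQRS test, as the sizing implies, and that all participants have the event. The check concerns only whether the significance levels agree. How well a continuous-time formula serves the planned discrete-time Cox model is a separate question.

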### Brief Summary of Research (250-400 words):

#### 1) Objectives:

##### *Research Question:*

Specific Aims 1: To assess cognitive recovery in a group of adults by undertaking baseline and follow-up testing after the administration of general anesthesia in healthy volunteers, 40–80 years old.

Specific Aims 2: To evaluate alterations in resting state and activity driven brain networks using fMRI, DTI, and ASL to characterize these same volunteers before and during recovery from the administration of general anesthesia.

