SA2: A sample size of 72 maintains 80% power for 30 MRI components to detect a change of 0.04 in each component testing for variation across the age spectrum where the assumed standard deviation of age is 11.25 years, the SD of the normalized MRI component outcomes is 1.0, and the two-sided Type I error of 0.0017 to account for multiplicity of the 30 tests (Bonferroni correction). We recognize that in fMRI, multiple comparisons across massive numbers of voxels make it extremely difficult to formulate valid assumptions regarding variability. However, we are using summary measures for these components and have used a Bonferroni adjustment for power calculation.

We expect missing data to be low as the total time under observation is 30 days and all participants are expected to have returned to baseline cognitive function by 30 days. Preliminary data had 75% return to baseline at T+15 minutes and all by 7 days. Thus, outcomes are expected to be captured on the majority of subjects even if they do not attend all follow-up visits. However, to insure sufficient outcomes we will increase by 5.5% to 76 thus adding a participant to each age decade.

11. Scientific Limitations and Rationale for Design Decisions

The results will be a first step and cannot completely elucidate age-related differences in subjects and conditions associated with clinical indications for surgery. The study focuses on the main effect of anesthesia on cognitive recovery but cannot address the possibility that administration of anesthesia interacts in some way with what happens due to the surgery itself. There are multiple anesthetics in current use. This proposal includes a fairly standard combination of anesthetic agents. Additional agents cannot be accommodated in this model. Safety is a primary concern. The current design is focused on safety as opposed to results at any cost.

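### For the Aim 2 network components, the SAP tests and powers only how change varies with age and specifies no inference for the mean change from before anesthesia to recovery

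*SAP*

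**What the plan says.** Protocol section 1 (Objectives), Specific Aims 2, reads: "To evaluate alterations in resting state and activity driven brain networks using fMRI, DTI, and ASL to characterize these same volunteers before and during recovery". The contrast is within person, before against recovery. Age does not appear in the aim.

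SAP 10.2 starts from that contrast: "Change scores will be calculated for each of 20-25 components (characterizing resting state and activity driven brain networks) related to fMRI imaging at each" of the scheduled scans. It then turns to age: "These changes (expressed in standardized units) associated with age will be analyzed using GLMMS adjusted for participant characteristics as described for Aim 1". Multiplicity is handled in the analysis by the False Discovery Rate: "We will use the False Discovery Rate test to adjust for multiple comparisons".

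Two further imaging analyses are planned in SAP 10.2:

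- Five rCBF measures from ASL "will be generated for each of three time points and analyzed with GLMMS corrected for multiple comparisons as described above". The effect to be tested, time or age, is not stated.
- "fMRI components will be entered as covariates in the above-mentioned Cox discrete-time models for the primary outcomes", and likewise in the GLMMs of SAP 10.1, to relate the components to cognitive recovery and to age.

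SAP 10.3 (SA2) gives the power: "A sample size of 72 maintains 80% power for 30 MRI components to detect a change of 0.04 in each component", with the contrast described as "to detect a change of 0.04 in each component testing for variation across the age spectrum". The inputs are an age SD of 11.25 years, an outcome SD of 1.0 and a two-sided alpha of 0.0017.

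SAP 10 also promises descriptive summaries of all baseline and outcome data, with means and standard deviations where appropriate.

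**The concern.** The aim and the planned test concern different quantities. Read as a before/recovery contrast, the natural estimand of Aim 2 is the mean change of each component from the pre-anesthesia scan. The SAP tests the slope of that change on age. If a network shifts by the same amount in every volunteer, the slope is zero and the SAP's null hypothesis is exactly true, however large the shift.

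For the cognitive scales, SAP 10.1 has a separate GLMM for the time course. No counterpart is named for the network components. Whether networks are altered after anesthesia, and whether they have returned by day 1 or day 7, would therefore rest on unadjusted descriptive summaries or on post hoc tests. The protocol's Background says that no imaging data on recovery from anesthesia exist, so this is a basic question for the study. The follow-up scans that could answer it are already scheduled.

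**Working it through.** **Inputs.** From SAP 10.3 (SA2): n = 72, effect 0.04, age SD 11.25 years, outcome SD 1.0, 30 tests, two-sided alpha 0.05/30 = 0.00167, stated as 0.0017. Planned enrollment is 76. Two readings are assumed: 0.04 is in SD units per year of age, and the SD of 1.0 applies to the change scores.

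**Step 1: reproduce the SAP's power.** A slope of 0.04 per year corresponds to a correlation with age of r = 0.04 × 11.25 / 1.0 = 0.45. By the Fisher-z test:

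- atanh(0.45) = 0.4847
- 0.4847 × √(72 − 3) = 0.4847 × 8.307 = 4.026
- critical value at two-sided 0.0017 = 3.138
- power = Φ(4.026 − 3.138) = Φ(0.888) = 81.3%

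This agrees with the stated 80%. By noncentral t, the slope detectable with 80% power is 0.0389 if 1.0 is the total SD and 0.0432 if it is the residual SD; both round to 0.04. The stated power is therefore a power for the age slope.

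**Step 2: what the age-slope test does with a shared shift.** Write the change as μ + β(age − mean age) + error. The planned test has null β = 0, and μ does not enter it. This was checked with 100,000 simulated trials per setting (n = 72, ages uniform on 40-80, error SD 1.0, β = 0):

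| Shared shift μ | Age-slope test, alpha 0.0017 | Mean-change test, alpha 0.0017 | Age-slope test, alpha 0.05 | Mean-change test, alpha 0.05 |
|---|---|---|---|---|
| 0 | 0.13% | 0.16% | 4.9% | 4.9% |
| 0.5 SD | 0.14% | 83.1% | 4.9% | 98.7% |
| 1.0 SD | 0.19% | 100% | 5.0% | 100% |

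The age-slope column stays at alpha up to simulation error.

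**Step 3: what the same data could show about the mean change.** This uses a one-sample t test with noncentrality μ√n / 1.0. At n = 72 and alpha 0.05/30, power is 25% for 0.3 SD, 83% for 0.5 SD and over 99% for 0.8 SD. Power of 80% is reached at μ = 0.49 SD (check: 0.487 × √72 = 4.13, against a critical t of 3.27 on 71 df). At n = 76, power for 0.5 SD is 86%. If the mean-change and age-slope tests were pooled and Bonferroni-split over 60 tests, power for 0.5 SD at n = 72 would be 77%.

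The shift sizes are illustrative, since the documents give none. The calculation is for one scan without covariates, at the fixed alpha of SAP 10.3. Under the planned False Discovery Rate, the threshold for each test depends on the results for the other components.

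**The case against.** Several points on the other side have force.

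- **The aim states no hypothesis.** Its verbs are about evaluating and characterizing. Protocol Aim 1 also omits age, yet SAP 10.1 makes age its primary goal, so the age focus is consistent across both aims. The mismatch may lie in the wording of the objective, between a SAP dated 2013 and a protocol revised in 2018. This stands, and restating Aim 2 would be a legitimate cure.
- **A shared shift would not be hidden.** The summaries in SAP 10 would display it, and a mean, an SD and n give an interval. This also stands. What is missing is a prespecified estimate, test and multiplicity family.
- **The GLMM already contains a mean change.** It does, through its intercept or time term, but the SAP does not name that quantity as a target. With uncentered age, the intercept is the change at age zero.
- **Not all of SAP 10.2 is about age.** The rCBF model may test time, and the components also enter the recovery models. A reader might infer that the whole imaging plan tests only age variation. The documents do not support that, so the point is confined to the network components and the unnamed rCBF effect. The recovery models do not test whether networks changed.
- **A slope test that rejects at alpha when the slope is zero is working properly.** A reader might take the gap in the simulation as power lost by a defective test. It is not: the two tests address different hypotheses.

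The supplied SAP is also an excerpt. Its Section 4, which sets the time points, is not available, so the exact scan contrasts cannot be checked.

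**Conclusion.** The point holds in a limited form. For the 20-25 network components, SAP 10.2-10.3 specifies and powers only the association of change with age. The mean change from the pre-anesthesia scan, which is the contrast in Protocol Aim 2, has no specified test, interval or power. The planned test cannot detect a change common to all ages; the descriptive summaries can show it, without error control. For rCBF the gap is one of ambiguity, because the tested effect is not named.

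On size: the stated 80% is reproduced (81%) as power for the age slope and says nothing about mean change. With SD 1.0 and alpha 0.05/30, 72 participants would give about 80% power for a mean change of about 0.49 SD, so the data could answer the question for moderate shifts. This rests on the two readings of SAP 10.3 given with the inputs. The documents do not say how large a shift to expect, so no claim is made that a shared alteration is the likely result.

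This should be corrected. It leaves the age analysis itself intact.

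**What to change.** In SAP 10.2:

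- Center age, for example at the sample mean.
- From the GLMMs already planned, estimate for each component the mean change from the pre-anesthesia scan at each later scan, with a 95% confidence interval and a test. Put these tests in their own False Discovery Rate family.
- Keep the age slope as a separate question.
- For rCBF, name the tested effects (time and age).

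In SAP 10.3, state that the 80% power applies to age variation only; the 0.49 SD figure can be added for reference with its assumptions.

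If the sponsor intends age variation alone, restate Protocol Aim 2 as age-related change instead.

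The cost is SAP wording and one extra estimate per measure and scan, with no new data or participants. The downsides are a second family of tests and a limit on interpretation: with no control arm, the mean change includes any retest effect and cannot by itself be attributed to anesthesia. The report should say so.

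### The Aim 2 power statement lists no covariate R² with age, although the Aim 2 models are adjusted as in Aim 1; with the SAP's own R² of 0.2, power at 0.04 is about 71%, not 80%

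*SAP*

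**What the plan says.** SAP section 10.3 gives three calculations, all with 72 participants and age as the predictor.

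- **Aim 1, primary (Cox):** coefficient 0.033, age SD 11.25 years, alpha 0.05, 80% power, other characteristics with a generalized R² of 0.2.
- **Aim 1, NIH Toolbox (Cox):** coefficient 0.041, alpha 0.05/6, and "other covariates having a generalized R^2 of 0.2 with age".
- **Aim 2 (imaging):** "SA2: A sample size of 72 maintains 80% power for 30 MRI components to detect a change of 0.04 in each component". The age SD is again 11.25 years, and the two-sided alpha is 0.0017 (Bonferroni for 30 tests). For the outcome, the SAP assumes that "the SD of the normalized MRI component outcomes is 1.0". No R² is listed.

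On the Aim 2 analysis, section 10.2 says that the age-related imaging changes "will be analyzed using GLMMS adjusted for participant characteristics as described for Aim 1".

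**The concern.** When covariates are correlated with age, the age coefficient is estimated less precisely: its variance is multiplied by 1/(1 − R²). The SAP recognises this for Aim 1. Aim 2 has the same predictor, sample and adjustment set, so the same inflation would be expected there, yet the listed inputs omit it and no reason is offered.

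The statement covers all 30 imaging tests in one of the study's two specific aims. If its 80% does not follow from the SAP's own assumptions, a null imaging result would be read against a type II error of 20% at 0.04, when those assumptions imply about 29%.

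**Working it through.** **Inputs (SAP 10.3).** n = 72; slope b = 0.04, read as SD per year because it is paired with the SD of age; SD(age) = 11.25; SD(outcome) = 1.0, read as the total SD; two-sided alpha 0.0017 (0.05/30 = 0.00167). R² = 0.2 comes from the Aim 1 calculations.

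**Step 1. Does Aim 1 include the R²?** Required N = (z₁₋α/₂ + z₀.₈)² / [β² × 11.25² × (1 − R²)].

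- Primary: (1.960 + 0.842)² / (0.033² × 11.25² × 0.8) = 71.2. Without R²: 56.9.
- Toolbox: (2.638 + 0.842)² / (0.041² × 11.25² × 0.8) = 71.1. Without R²: 56.9.

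With the printed coefficients, both reach 72 only when R² = 0.2 is included. The hazard ratios are too coarsely rounded for this check: ln 1.03 = 0.0296 without R² happens to give 71.0, but ln 1.04 = 0.0392 gives 62.2 without and 77.8 with. The text states the R² in both cases.

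**Step 2. Reproduce the Aim 2 figure without R².** Implied correlation r = 0.04 × 11.25 / 1.0 = 0.45.

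- Fisher z test of r: power 81.3%; N for 80% power = 71. This matches the SAP.
- Slope t-test: residual SD = √(1 − 0.45²) = 0.893. Noncentrality = 0.45 × √72 / 0.893 = 4.276; critical t on 70 df = 3.264; power 83.8%. Power is 80% at a slope of 0.0389.

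**Step 3. Add R² = 0.2.** The noncentrality is multiplied by √(1 − 0.2) = 0.894: 4.276 × 0.894 = 3.824.

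| Convention (total SD 1.0, n = 72, slope 0.04) | Power with R² = 0.2 |
|---|---|
| Slope t-test, residual SD 0.893 | 70.9% |
| Same, normal approximation | 75.4% |
| Residual variance 1 − 0.2025 × 0.8 = 0.838, t | 67.8% |
| Same, normal approximation | 72.3% |
| Fisher z, two ways of applying R² | 68.8%, 65.7% |

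None reaches 80%.

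**Step 4. Restate on the slope t-test basis (first row).**

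- With 72, 80% power is reached at a slope of 0.0425 (0.0413 by normal approximation).
- With all 76 analysed, power at 0.04 is 74.5%, and the 80% slope is 0.0415.
- For scale only: 80% power at exactly 0.04 would need 83.

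**The case against.** **Rounding.** The effect is printed to one significant figure. The 80% slope is 0.0389 without R² and 0.0425 with it, and both print as 0.04. This stands: the printed figure alone cannot show whether the term was used. A reader might infer a proven arithmetic error. The documents do not support that. What is secure is that an assumption applied twice in Aim 1 is absent from the Aim 2 inputs, and that power at the printed 0.04 falls below 80% once it is applied.

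**Total or residual SD.** If 1.0 were the residual SD, power with R² = 0.2 would be 56% by the t-test (60% with 76), and the 80% slope would be 0.0483. A reader might quote these figures. However, the SAP describes 1.0 as the SD of the component outcomes, which reads naturally as the total SD. On the residual reading, power at 0.04 is already 71% without any R², so R² would not be the only cause of the shortfall.

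**Actual power under the planned analysis.** Section 10.2 plans mixed models over several time points and false discovery rate control; Bonferroni is used for the power calculation. Covariates may also explain outcome variance. Any of these could raise power. For example, assuming the Benjamini-Hochberg procedure, the threshold for the third-ranked of 30 tests is 0.05 × 3/30 = 0.005, and power at 0.04 with R² = 0.2 is then 82% by the same t-test. This also stands: it would be wrong to conclude that the imaging tests will really have less than 80% power. But the SAP gives no within-person correlation, no variance explained by covariates and no expected number of true effects, so none of this supports its 80% as written.

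**Conclusion.** The point holds in a limited form. Under the SAP's own R² of 0.2, the stated 80% power at 0.04 is not delivered. It is about 71% with 72 participants (66% to 75% by convention) and 74.5% with 76. Equivalently, the slope detectable with 80% power moves from 0.0389 to about 0.0425, a modest change.

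This rests on four assumptions: 0.04 is SD per year of age; 1.0 is the total outcome SD; the test is of a single-measurement slope at two-sided alpha 0.0017; and the Aim 1 R² carries over because the adjustment set is the same. It is a gap in the power statement. It does not show that the study is too small or that the planned imaging analysis is wrong.

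**What to change.** In SAP section 10.3, for Aim 2:

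1. Apply R² = 0.2 as in Aim 1, or say why it does not apply.
2. Restate the result as 80% power for a slope of about 0.0425 SD per year with 72 (0.043 when rounded up; 0.0415, or 0.042, with 76), or as about 71% power at 0.04 (74.5% with 76).
3. Give the slope to three decimals with its unit, and confirm that 1.0 is the total SD.
4. If repeated measures, prognostic covariates or false discovery rate control are relied on to recover power, state the values assumed.

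Enrolment, visits and analysis do not change. The only cost is a slightly less favourable stated figure.
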